### 3.3.3 Exclusion criteria

1. Cataract surgery performed within 6 months prior to screening or planned during the trial in the study eye; or any additional eye disease in the study eye that, in the opinion of the investigator, could compromise or alter visual acuity during the course of the study (e.g. vein occlusion, uncontrolled intraocular pressure (IOP) >24 mmHg on optimal medical treatment, glaucoma with visual field loss, uveitis or other ocular inflammatory disease, vitreomacular traction, monocular vision, history of ischemic optic neuropathy, or genetic disorders such as retinitis pigmentosa)
2. Active center-involved DME (CI-DME) on clinical examination and OCT central subfield thickness in the study eye above 300 µm as measured by Optovue OCT or above 320 µm as measured by Heidelberg OCT.
3. Anterior segment and vitreous abnormalities in the study eye that would compromise the adequate assessment of the best corrected visual acuity or an adequate examination of the posterior pole
4. Evidence of neovascularization on clinical examination including active neovascularization of the iris (small iris tufts are not an exclusion) or angle neovascularization in the study eye, ruled out by gonioscopy (documented in the last 4 weeks before screening or performed at screening)
5. Prior pan-retinal photocoagulation (defined as  $\geq 100$  burns placed previously outside of the posterior pole) in the study eye
6. Treatment of either CI-DME or DR with macular laser within 3 months prior to screening, or intraocular injections of medication within 6 months prior to screening, and no more than 4 prior intraocular injections in the study eye at any time in the past
7. Patients treated with MAO inhibitors or drugs that may have potential side effects due to MAO inhibition, as described in [Section 4.2.2.1](#).
8. Current or planned, during the trial, use of medications known to be toxic to the retina, lens or optic nerve, or cause vision loss (see [Section 4.2.2.1](#))
9. Patients who must or wish to continue the intake of other restricted medications (see [Section 4.2.2.1](#)) or any drug considered likely to interfere with the safe conduct of the trial
10. Estimated Glomerular filtration rate (eGFR)  $< 60$  mL/min/1.73m^2 calculated by Chronic Kidney Disease Epidemiology Collaboration (CKD-EPI) equation at screening, or where the investigator expects filtration rate is likely to drop below 60 mL/min/1.73m^2 during the trial

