### **4.2.2 Restrictions, warnings and precautions**

#### **4.2.2.1 Restrictions regarding concomitant treatment**

The following medications are prohibited 5 weeks prior to BI 1467335 dosing and during study participation. In addition BI 1467335 should be discontinued for at least 14 days prior to starting a chronic treatment with these same agents:

- Antidepressants
  - Tricyclic antidepressants such as butriptyline, clomipramine, imipramine, trimipramine, desipramine, dibenzepin, lofepramine, maprotiline, nortriptyline, amitriptyline, amitriptylinoxide, amoxapine, demexiptiline, dimetacrine, dosulepin,

- doxepin, fluacizine, imipraminoxide, melitracen, metapramine, nitroxazepine, noxiptiline, pipofezine, propizepine, quinupramine, amineptine, iprindole, pipramol, tianeptine
- Selective serotonin reuptake inhibitors (SSRIs) such as fluoxetine, fluvoxamine, sertraline, citalopram, escitalopram and paroxetine
- Serotonin-norepinephrine reuptake inhibitors (SNRIs) such as venlafaxine, duloxetine, atomoxetine, desvenlafaxine, levomilnacipran, milnacipran, sibutramine
- MAO Inhibitors
  - Nonselective MAO-A/MAO-B inhibitors such as isocarboxazid, nialamide, phenelzine, hydracarbazine and tranylcypromine.
  - Selective MAO-A inhibitors such as bifemelane, moclobemide, pirlindole, and toloxatone.
  - Selective MAO-B inhibitors such as rasagiline, selegiline and safinamide.

The following medications are prohibited 2 weeks prior to BI 1467335 dosing and during study participation:

- Meperidine
- Tramadol
- Methadone
- Propoxyphene
- Dextromethorphan
- Cyclobenzaprine
- Sympathomimetic medications including nasal, oral and ophthalmic decongestants and cold remedies
- Bupropion, triptans (almotriptan, rizatriptan, sumatriptan, zolmitriptan, oxitriptan), linezolid, tedizolid, methylene blue, lithium and pethidine

The following drugs are prohibited during the entire duration of the trial:

- Drugs that may affect the retina or the optic nerve, such as quinolones, thioridazine, deferoxamine, ethambutol or vigabatrin: at the time of screening and during the trial.
- Amidarone, methotrexate, systemic glucocorticoids, tetracyclines, tamoxifen, estrogens (excluding oral contraception), anabolic steroids and valproic acid and any medication which prolongs QT time
- Initiation of intensive insulin therapy (switch from regular injections to pump)

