6.2 IMPORTANT PROTOCOL DEVIATIONS

A protocol deviation (PD) is important if it affects the rights or safety of the study subjects, or if it can potentially influence the primary outcome measurement(s) in a non-negligible way.

A list of important PDs (iPD) for this trial is given [Table 6.2: 1](#). Important PDs will be reviewed at Medical Quality Review Meetings (MQRM) conducted periodically during the trial. Other iPDs identified during MQRMs, Blinded Report Planning Meetings (BRPM), or during review of BI CTMS issues reports may supplement this list. The decision to exclude

subjects with certain iPDS from analyses will be finalized at the last BRPM prior to database lock.

Table 6.2: 1 Important protocol violations

Category / Code	Description	Comment	Excluded from
A	Entrance criteria not met		
A1	Inclusion criteria not met		
A1.1	Age at enrollment <18 years	Inclusion criterion 1 not met or age <18 years on demographics eCRF	None
A1.2	Female patient of childbearing potential not using required contraception	Inclusion criterion 2 not met	None
A1.3	No diagnosis of Type 1 or Type 2 diabetes	Inclusion criterion 3 not met	PPS
A1.4	HbA1c > 12% at screening	Inclusion criterion 4 not met	None
A1.5	Diagnosis of NPDR without CI-DME at screening not met	Inclusion criterion 5 not met	PPS
A1.6	BCVA ETDRS letter score < 70 letters in each eye at screening	Inclusion criterion 6 not met	PPS
A1.7	Inadequate retinal examination parameters	Inclusion criterion 7 not met	PPS
A2	Exclusion criteria met		
A2.1	Additional eye disease in the study eye that may compromise visual acuity	Exclusion criterion 1 met	PPS
A2.2	Active CI-DME and OCT central subfield thickness > 300 µm in study eye	Exclusion criterion 2 met	PPS
A2.3	Anterior segment and vitreous abnormalities in the study eye	Exclusion criterion 3 met	PPS
A2.4	Evidence of neovascularization in the study eye	Exclusion criterion 4 met	PPS
A2.5	Prior pan-retinal photocoagulation in the study eye	Exclusion criterion 5 met	PPS
A2.6	History of DME or DR treatment: macular laser within 3 months prior to screening, intraocular injections within 6 months prior to screening, or >4 prior injections in study eye	Exclusion criterion 6 met	PPS
A2.7	Treatment with MAO inhibitors or drugs with potential side effects due to MAO inhibition	Exclusion criterion 7 met	None
A2.8	Current or planned use of restricted medications	Exclusion criteria 8 or 9 met	PPS

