A2.9	Glomerular filtration rate (eGFR) < 60 mL/min/1.73m ² at screening or expected during trial	Exclusion criterion 10 met	None
A2.10	ALT or AST > 2x ULN or total bilirubin > 1.5x ULN	Exclusion criterion 11 met	None
A2.11	Excluded medical condition	Exclusion criteria 12, 13, 14, 15, 16 or 23 met	None
A2.12	Significant substance abuse	Exclusion criterion 17 met	None

Table 6.2: 1 Important protocol violations (cont.)

Category / Code	Description	Comment	Excluded from
	A2.13	Hypersensitivity to trial drug or allergy to fluorescein dye	Exclusion criterion 18 met
	A2.14	Major surgery performed within 12 weeks prior to randomization or planned during trial	Exclusion criterion 19 met
	A2.15	Current enrollment in, or < 30 days or 5 times half-life of the investigational drug since participating in, another investigational drug trial	Exclusion criterion 20 met
	A2.16	Previous randomization in this trial	Exclusion criterion 21 met
	A2.17	Women who are pregnant, nursing, or who plan to become pregnant during the trial	Exclusion criterion 22 met
B	Informed consent		
	B1	Informed consent not available/not done	Inclusion criterion 8 not met; informed consent date or signature missing
	B2	Informed consent given late	Study informed consent date after date of any study-related procedure; biobanking informed consent date after sample collection date; or re-consent given late.
C	Trial medication and randomisation		
C1	Incorrect trial medication taken		
	C1.1	No study medication taken	Patient randomized but no evidence of study medication taken
	C1.2	Incorrect trial medication taken	Incorrect medication taken for >20% of treatment duration or > 20% of last dose interval before primary endpoint assessment as identified after database lock by comparison of assigned drug kit number from IRT with drug kit number recorded in eCRF. [manual review]
C3	Non-compliance		
	C3.1	Non-compliance with trial medication	Mean overall treatment compliance across treatment duration for an individual <80% or >120%.
C4	Medication code broken		
	C4.1	Medication code broken at site without just cause	Medication code broken for reasons other than those documented in CTP Section 4.1.5.2. [manual review]

Table 6.2: 1 Important protocol violations (cont.)

Category / Code		Description	Comment	Excluded from
D		Concomitant medication		
	D2	Use of prohibited concomitant medication	Reported use of prohibited concomitant medications, defined in CTP Section 4.2.2.1[manual review]	PPS
F		Trial specific		

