6.3 PATIENT SETS ANALYSED

The following patient analysis sets are defined for this trial:

- Screened set (SS): includes all patients who sign informed consent
- Randomized set (RS): includes all patients who sign informed consent, are screened for the trial and are randomized to trial medication, regardless of whether any trial medication is administered.
- Treated set (TS): includes all patients who sign informed consent, are dispensed trial medication and are documented to have taken at least one dose of trial medication (BI 1467335 or placebo). Safety analyses, including the analyses of the primary endpoint of ocular adverse events and secondary endpoint of non-ocular adverse events, and summaries of demographics and baseline characteristics will be based on the TS.
- Full analysis set (FAS): includes all patients in the TS with non-missing baseline and at least one non-missing on-treatment measurement for DRSS or BVCA. Patients in

FAS are analyzed according to the intent-to-treat principle, i.e. patients in FAS are analyzed according to the trial medication assigned at randomization.

- Per protocol set (PPS): includes all patients from the FAS who do not have an iPD resulting in exclusion from the PPS.
- [REDACTED]
- ECG analysis set (ECGS): includes all subjects in TS who have at least one baseline and one post-baseline measurement for at least one ECG interval endpoint.

Analyses relevant to each patient set are shown in [Table 6.3: 1](#).

Table 6.3: 1 Patient sets analyzed

Class of endpoint	Patient set					
	SS	RS	TS	FAS	PPS	[REDACTED]
Primary and secondary safety endpoints			X			
Secondary ophthalmologic endpoint				X	X	
Further ophthalmic endpoints				X		
Safety endpoints			X			
[REDACTED]						[REDACTED]
ECG endpoints						X
Demographic/baseline endpoints			X			
Important protocol deviations		X				
Disposition	X					

[REDACTED]

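### SAP Table 6.2: 1, row D2 has no end date, so a prohibited medicine first used after the Week 12 DRSS image still lists the patient for exclusion from the per-protocol repeat of that analysis

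*SAP*

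**What the plan says.** SAP 6.2, Table 6.2: 1, row D2 is triggered by "Reported use of prohibited concomitant medications, defined in CTP Section 4.2.2.1". It is flagged for manual review and its last column reads PPS. No date limit is given.

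Protocol 4.2.2.1 has three drug lists:

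- Antidepressants and MAO inhibitors are "prohibited 5 weeks prior to BI 1467335 dosing and during study participation". A further sentence asks that trial drug be stopped at least 14 days before chronic treatment with these agents begins.
- A second list is banned from two weeks before dosing and then for as long as the patient is in the study. It includes tramadol, dextromethorphan and "Sympathomimetic medications including nasal, oral and ophthalmic decongestants and cold remedies".
- The third list opens with "The following drugs are prohibited during the entire duration of the trial" and covers quinolones, tetracyclines, systemic glucocorticoids and others.

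Anti-VEGF treatment is restricted separately, and only alongside trial drug.

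Protocol 6.2.3 makes FU3, 12 weeks after the last dose, the final visit. SAP 6.3 defines the set as follows: "Per protocol set (PPS): includes all patients from the FAS who do not have an iPD resulting in exclusion from the PPS". Table 6.3: 1 marks the PPS for the secondary ophthalmologic endpoint only, and SAP 7.5.2 repeats that section's analyses on the PPS. The endpoint is a DRSS improvement of at least 2 steps at Week 12. SAP 6.2 leaves the final decision on exclusions to the last BRPM before database lock.

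**The concern.** A per-protocol exclusion is meant to remove outcomes that a deviation may have distorted. A completer who takes a cold remedy at Week 20 had the Week 12 fundus image taken about 8 weeks earlier. The remedy cannot have altered that grade, yet D2 as written lists the patient for exclusion. A valid Week 12 outcome is lost and the Week 12 comparison gains nothing.

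The PPS repeat is the only visible check on the secondary DRSS result, and SAP section 4 expects no more than 3 patients with a 2-step improvement. With so few events, one unnecessary exclusion can visibly change the result. Medication use in follow-up may also depend on how a patient fared on treatment, so these exclusions need not fall equally on the two arms. The documents do not show that they would be unequal.

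**Working it through.** **1. The plan's own figure.** Protocol 7.7 gives about 80% for seeing the improvement in 2 patients, assuming 6% response on active and 0% on placebo, with 50 patients per group. Read as at least 2:

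P(X ≥ 2), X ~ Bin(50, 0.06) = 1 − 0.94^50 − 50 × 0.06 × 0.94^49 = 0.810.

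This reproduces the stated figure. Exactly 2 would give 0.226, so the plan means at least 2. Expected responders: 0.06 × 50 = 3, in line with SAP section 4.

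**2. How much of D2's reach lies after the outcome.** The EOT visit is Day 85 with a window of +6 days, so dosing to EOT spans 84 to 90 days. FU3 is at last dose + 84 ± 6 days, so follow-up spans 78 to 90 days.

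- Planned: 84 / (84 + 84) = 50%
- Lowest: 78 / (90 + 78) = 46%
- Highest: 90 / (84 + 90) = 52%

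About half of the post-dose period that D2 covers comes after Week 12.

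**3. Which drugs can trigger D2 late.**

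| Restriction in Protocol 4.2.2.1 | First use after Week 12 |
|---|---|
| Two-week list | Prohibited until FU3, so D2 applies |
| Whole-trial list | Prohibited until FU3, so D2 applies |
| Antidepressants and MAO inhibitors | Unclear: the ban covers participation, but the 14-day sentence foresees chronic use after trial drug stops |
| Anti-VEGF | Not prohibited after trial drug stops, so D2 does not apply |

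**4. Effect of one exclusion on the active arm.** Starting from 3/50 = 6.0%:

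- a non-responder removed (94% likely if use is unrelated to response): 3/49 = 6.1%
- a responder removed (6% likely): 2/49 = 4.1%

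**5. Range over assumed rates.** The documents give no rate. Let r be the assumed share of patients whose only prohibited use started after the Week 12 image. Assume that use is independent of response, that there are no other PPS exclusions, and that the BRPM corrects no case.

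- Chance of losing at least one of 3 responders = 1 − (1 − r)^3
- Chance of at least 2 responders in the active PPS arm = P(X ≥ 2), X ~ Bin(50, 0.06(1 − r))

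| r (assumed) | Patients listed, of 100 | Lose ≥ 1 of 3 responders | P(≥ 2 responders in active PPS) |
|---|---|---|---|
| 0 | 0 | 0 | 0.810 |
| 0.01 | 1 | 0.030 | 0.805 |
| 0.05 | 5 | 0.143 | 0.786 |
| 0.10 | 10 | 0.271 | 0.760 |
| 0.20 | 20 | 0.488 | 0.699 |

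Patients who also used a listed medicine before the Week 12 image do not count towards r. They stay excluded under any sensible rule.

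**The case against.** **Case review is already planned.** D2 carries a manual review flag, exclusions are settled at a masked meeting, and SAP 6.2 calls a deviation important only if it touches rights or safety or could influence the primary outcome. A Week 20 cold remedy might never be classed as important. This stands as a limit on the consequence: the table in step 5 is a worst case. It does not change the disposition written in the row, which reviewers would have to override patient by patient.

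**Post-Week-12 data may be used.** SAP 7.5.2 allows, if there are enough events, a logistic model adjusted for visit with odds ratios at each time point, repeated on the PPS. Follow-up visits could enter, and late use could affect those. This stands, and the fix deals with it by dropping visits rather than patients.

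**Row C1.2 is a weak precedent.** That row is limited to treatment duration or "20% of last dose interval before primary endpoint assessment". But it concerns trial medication, which is taken only in the treatment period, and the primary endpoint is ocular adverse events over 24 weeks, not Week 12 DRSS. Agreed: the point does not rest on it.

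**Low stakes.** The trial is exploratory, and the primary endpoint and FAS results do not depend on D2. This stands.

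**A stronger reading that fails.** A reader might infer that D2 contradicts row A2.7, which covers "Treatment with MAO inhibitors or drugs with potential side effects due to MAO inhibition" and carries no exclusion, although exclusion criterion 7 ("Patients treated with MAO inhibitors or drugs that may have potential side effects due to MAO inhibition, as described in") points to the same Protocol 4.2.2.1. The documents do not support this. A2.7 codes a breach at entry and D2 codes use. Under SAP 6.3 a single PPS-coded deviation removes the patient, so someone who enters on such a drug and continues it is removed under D2. The rows give one answer.

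**Conclusion.** The timing point holds. For the two-week and whole-trial lists, D2 as written lists for PPS exclusion patients whose only prohibited use began after the Week 12 DRSS image. For antidepressants and MAO inhibitors the same may apply, but the 14-day sentence leaves it open whether late use is a deviation at all.

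The size is small and cannot be fixed from the documents. It is nil if nobody uses a listed medicine for the first time in follow-up. If one responder were lost, 3/50 (6.0%) would become 2/49 (4.1%). At assumed rates of 1% to 20%, the chance of losing at least one of 3 responders is 3% to 49%, given independence from response and no correction at the BRPM. The FAS and Treated Set analyses are unaffected.

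A reader might also infer that the ban itself runs too long. That does not follow: Protocol 5.2.6.2.1 treats the whole follow-up as the residual effect period, so a restriction until FU3 is coherent and late use is properly reported as a deviation. Only its consequence for the PPS is at issue.

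**What to change.** Add to SAP Table 6.2: 1, row D2:

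> *PPS exclusion applies only if the prohibited use started on or before the date of the patient's Week 12 DRSS assessment (or Day 91 if there is none), including use within the pre-dose prohibition periods. Use that started only later is reported as an important deviation, Excluded from: None.*

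Day 91 is Day 85 plus the 6-day visit window. The sentence sets an end date and leaves the start of D2's reach alone, so use during screening only (a systemic glucocorticoid, for example) stays covered. Early discontinuers who start a listed drug before Day 91 and have no Week 12 assessment also stay covered.

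If the optional visit-adjusted logistic model includes follow-up visits, omit that patient's visits after the drug start and keep the earlier ones.

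The cost is one more date check at the BRPM, using concomitant therapy start dates that are already collected. The drug restrictions, trial conduct, sample size, and FAS and Treated Set analyses do not change, and no protocol amendment is needed.

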6.3 PATIENT SETS ANALYSED

The following patient analysis sets are defined for this trial:

- Screened set (SS): includes all patients who sign informed consent
- Randomized set (RS): includes all patients who sign informed consent, are screened for the trial and are randomized to trial medication, regardless of whether any trial medication is administered.
- Treated set (TS): includes all patients who sign informed consent, are dispensed trial medication and are documented to have taken at least one dose of trial medication (BI 1467335 or placebo). Safety analyses, including the analyses of the primary endpoint of ocular adverse events and secondary endpoint of non-ocular adverse events, and summaries of demographics and baseline characteristics will be based on the TS.
- Full analysis set (FAS): includes all patients in the TS with non-missing baseline and at least one non-missing on-treatment measurement for DRSS or BVCA. Patients in

FAS are analyzed according to the intent-to-treat principle, i.e. patients in FAS are analyzed according to the trial medication assigned at randomization.

- Per protocol set (PPS): includes all patients from the FAS who do not have an iPD resulting in exclusion from the PPS.
- [REDACTED]
- ECG analysis set (ECGS): includes all subjects in TS who have at least one baseline and one post-baseline measurement for at least one ECG interval endpoint.

Analyses relevant to each patient set are shown in [Table 6.3: 1](#).

Table 6.3: 1 Patient sets analyzed

Class of endpoint	Patient set					
	SS	RS	TS	FAS	PPS	[REDACTED]
Primary and secondary safety endpoints			X			
Secondary ophthalmologic endpoint				X	X	
Further ophthalmic endpoints				X		
Safety endpoints			X			
[REDACTED]						[REDACTED]
ECG endpoints						X
Demographic/baseline endpoints			X			
Important protocol deviations		X				
Disposition	X					

[REDACTED]

6.5 POOLING OF CENTRES

This section is not applicable because center/country is not included in the statistical model.

6.6 HANDLING OF MISSING DATA AND OUTLIERS

Techniques for handling missing data are described in Section 7.5 of the CTP. Missing and incomplete adverse event dates will be handled according to BI standards (5). The handling of missing PK data and values reported as NOS, NOR, NOA or BLQ are described in Section 10.1 of the CTP.

For efficacy analyses, missing data will not be imputed. Mixed effect models will handle missing data based on a likelihood methods under the “missing at random” assumption. No imputations of missing AEs, laboratory data or vital signs data are planned. For binary efficacy endpoints, patients with missing data in the study eye at the time point of interest will be considered non-responders, i.e. failure to achieve the defined endpoint.

For ECG data, if single cardiac cycles of an ECG (out of three) are missing, the arithmetic mean for this single ECG will be calculated with the reduced number (1 or 2) of cycles.

For the classification of the on-treatment QTc/QT intervals into ‘no new onset’ / ‘new onset’ categories, a missing value is obtained only in the case that

- i. all on-treatment values are missing, and
- ii. the baseline value is less than or equal to 500 msec, or missing.

If condition (i) is fulfilled but the baseline value is greater than 500 msec, this case will be categorized as ‘no new onset’. If baseline is missing and the maximum on-treatment QTc interval is greater than 450 msec (or 500 msec for QT interval, respectively), this is classified as a ‘new onset’ in the respective category. If baseline is missing and the maximum QTc interval is less than or equal to 450 msec (or 500 msec for QT interval, respectively), this will be categorized as ‘no new onset’. If baseline is missing, a QTc/QT interval > 500 msec at any time on treatment will be a notable finding.

For patients on active drug, missing plasma concentration values with ‘BLQ’ in the comment field will be replaced by $\frac{1}{2}$ LLOQ.

